To assess the longitudinal effect of MEDI3506 compared with placebo on lung function in adult participants with uncontrolled moderate-to-severe asthma.	As measured in clinic, change from baseline in pre-BD FEV1 to Weeks 1, 4, 8, 12, 20, and 24.
To assess the acute effect of MEDI3506 compared with placebo on pre-BD FEV1 in adult participants with uncontrolled moderate-to-severe asthma.	As measured in clinic, change in pre-BD FEV1 (L) from pre-administration of study intervention to 4 hours post-administration of MEDI3506 or placebo at Day 1.
To assess the effect of MEDI3506 compared with placebo on asthma control in adult participants with uncontrolled moderate-to-severe asthma.	During the intervention period (baseline to Week 16): 
 • Annualised rate of asthma exacerbations. • Annualised rate of hospitalised asthma exacerbations.
To assess the longitudinal effect of MEDI3506 compared with placebo on asthma control and health status in adult participants with uncontrolled moderate-to-severe asthma.	Change from baseline to Weeks 1, 4, 8, 12, and 24 in ACQ-6 score. Change from baseline to Weeks 4, 12, and 24 in SGRQ score. Change from baseline up to Week 24 in 2-weekly mean daily rescue medication usage (puffs/day). Change from baseline to Weeks 4, 8, 12, 16, 20, and 24 in: 
 • Asthma symptom score. • Mean number of night-time awakenings.
To assess the benefit-risk profile of MEDI3506 as perceived by adult participants with uncontrolled moderate-to-severe asthma.	PGI-BR at Week 16.
To evaluate CCI and inflammatory blood biomarkers that may predict an efficacy response to MEDI3506 in adult participants with uncontrolled moderate-to-severe asthma.	CCI  Association of allergen-specific IgE status with primary and secondary efficacy endpoints at Week 16.
To assess the effect of MEDI3506 compared with placebo on asthma related inflammatory airway biomarkers in adult participants with uncontrolled moderate-to-severe asthma.	Percent change from baseline to Weeks 1, 4, 8, 12, 16, 20, and 24 in concentration of FeNO. Change from baseline to Weeks 4, 8, 12, 16, 20, and 24 in exploratory biomarkers measured in nasal lining fluid. Change from baseline to Week 16 in mRNA nasal transcriptome.

Table 4 Objectives and Endpoints

Objective	Endpoint

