3.1.4 Analysis visit and study phase windows

For the exacerbation and CompEx related analyses no analysis visit windows will be applied.

For PK related analyses no analysis visit windows will be applied and the actual visits and timepoints will be used instead.

Visit windows will be used for all assessments to allow for by-visit analyses, since not all assessments might be performed on the scheduled day. Unless specified otherwise, the efficacy and safety analyses will be based on the analysis visit windows. The actual assessment day will be mapped to the planned study visit following the analysis visit windowing rules below:

- If more than one assessment falls within a visit window, the closest non-missing assessment to the scheduled day will be used in the analysis.
- If more than one non-missing assessment actual dates are equidistant from the target day, the earlier assessment will be used in the analysis.
- If more than one assessment is selected (i.e. due to teste repetitions) the average for numerical values / worst case for categorical values will be used in the analysis

The visit windows for the visits following baseline are constructed in such a way that the upper limit of the interval falls half way between the two visits, rounded up to the nearest integer. The lower limit of each window will be the mean of the two adjacent planned study days +1, rounded up to the nearest integer, except for the first post-treatment visit.

Table 3 Analysis visit windows for in-clinic spirometry, FeNO, vital signs, SARS-Cov-2 PCR test, exploratory biomarkers (serum)

Protocol Visit	Week	Analysis Visit	Scheduled Study Day	Visit Window for Analysis (Days)
SV4	Week 0	Baseline	1	All assessments prior to the first administration of investigational product
SV6	Week 1	Week 1	8	All assessments on or after the first administration of investigational product to Day 19
SV7	Week 4	Week 4	29	20 to 43
SV8	Week 8	Week 8	57	44 to 71
SV9	Week 12	Week 12	85	72 to 99
SV10	Week 16	Week 16	113	100 to 127
SV11	Week 20	Week 20	141	128 to 155
SV12	Week 24	Week 24	169	≥ 156

SV = Study Visit.

For vital signs, if the selected day is a dosing day, timepoints as per SOA within the day need to be considered (ie, Baseline, Day1: post-dose, Day1: 30m, Day1: 60m, Day1: 120m, Week1, etc...).

For in-clinic spirometry pre-BD at day 1 timepoint at 4 hour post dose need also to be considered.

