4.1.2 Repeated measures mixed effects analysis of covariance model (MMRM)

The repeated measures mixed effects analysis of covariance model (MMRM) will be used to fit change from baseline for continuous endpoints at each visit, for the ITT population. The model will include all available data from all visits up to and including the target visit, irrespective of whether the participant discontinued study intervention or received rescue therapy. No imputation will be made for missing data, as a repeated measures model is being applied. The model will include fixed effects for baseline, background medication use, geographic region, baseline ICS total daily dose, visit, treatment and the baseline by visit and treatment by visit interactions. Visits within subject are considered as repeated measurements. An unstructured covariance matrix will be used to describe the correlations between observations on a participant between visits. The denominator degrees of freedom will be calculated using the Kenward-Rogers method. In the event that the model with unstructured covariance matrix fails to converge, an autoregressive (1) covariance matrix will be used instead. If also the autoregressive (1) does not converge, a compound symmetry covariance matrix will be used. If the model still does not converge, the baseline by visit effect will be deleted from the model. Estimates of the least square mean change from baseline in endpoint variable for each treatment, and the difference between them, together with two-sided 80% confidence interval, will be obtained from the model for each visit. The significance of the treatment effect will be tested at a 10% one-sided level of significance as described in Section 4.1.1.

The reportable results from the model will be:

- The least-square means (LSMeans) change from baseline at certain visit and their standard errors for each group
- The difference in change from baseline at certain visit between active treatments groups and placebo (LSMeans difference) together with its two-sided 80% confidence interval (CI)
- The one-sided p-value for the difference in change from baseline at certain visit between active treatment groups and placebo

If the dependent variable is considered to be normally distributed, the variable fitted in the model will be the change from baseline; the MMRM and the reportable results will be those described above.

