4.1.3 Analysis of covariance (ANCOVA)

An ANCOVA model will be used to analyse change from baseline for continuous endpoints collected at only one post-baseline visit. The treatment group will be considered as a fixed effect of the model, with the baseline value, background medication use, geographic region and baseline ICS total daily dose as covariates. Comparisons of MEDI3506 **CC1** mg versus placebo and MEDI3506 **CC1** mg versus placebo will be assessed within the same model. The restricted maximum likelihood (REML) approach will be used for the estimation of the variance and covariance parameters of the linear model; one-sided difference test, with alpha level at 10% will be used for the treatment comparisons. No imputation will be made for missing data.

The reportable results from the model will be:

- The LSmeans and their standard errors for each treatment group;
- The difference between active treatment groups and placebo (LSmean difference) together with its two-sided 80% CI;
- The one-sided p-value for the difference between active treatment groups and placebo.

If the parameter results to be normally distributed, the variable fitted in the model will be the change from baseline; the ANCOVA model and the reportable results will be those described above.

On the other hand, if the parameter results to be log-normally distributed, the variable fitted in the model will be the change from baseline in logarithmical scale. Change from baseline in logarithmical scale is defined as the log-transformation of the post-baseline visit value minus the log-transformation of the baseline value.

The ANCOVA model will be as described above but the reportable results from the model will be:

- For the percent change:
 - Back transformed LSmeans for each group, which correspond to the estimated percent change from baseline; back transformed LSmeans is derived as $[\text{EXP}(\text{LSMean})-1]*100$;
 - Two-sided 80% CI of the back transformed LSmeans for each group; 80% CI of the back transformed LSmeans is derived as $[\text{EXP}(\text{Lower limit of the 80\% CI of the LSmean})-1]*100$; $[\text{EXP}(\text{Upper limit of the 80\% CI of the LSmean})-1]*100$;
- For the relative change:
 - Back transformed LSmeans for each group, which correspond to the estimated relative change from baseline; back transformed LSmeans is derived as $\text{EXP}(\text{LSMean})$;

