4.2.5 Analysis of secondary endpoints

4.2.5.1 Analysis of lung function parameters measured in clinic

The observed values and changes from baseline in lung function parameters measured in clinic such as pre-BD FEV₁, post-BD FEV₁, FVC, FEV₁/FVC, percent predicted FEV₁, percent predicted FVC, PEF and FEF_{25-75%} will be summarised by treatment group and visit for the ITT population. Observed values and changes from baseline in pre-BD FEV₁ to 4-hours post administration of IP at Day 1 will also be summarised.

The difference in mean change from baseline in post-BD FEV₁ to Weeks 8 and 16 will be estimated using a MMRM, similar to that described for the primary efficacy analysis (Section 4.1.2). The change from baseline through Week 16 will be included in the model. LS Mean change from baseline and two-sided 80% CI through Week 16 in post-BD FEV₁ will be presented in figures.

All lung function parameters measured in clinic will be also reported in listing using the ITT population.

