14.2 Efficacy evaluation data		
14.2 Spirometry		
Table 14.2.1.1	Lung function parameters measured in clinic by visit, summary statistics	ITT population
Table 14.2.1.2	Lung function parameters measured in clinic by visit and subgroup, summary statistics	ITT population
Table 14.2.1.3	Change from baseline to Week 16 in pre-BD FEV1 (as measured in the clinic) treatment comparisons, MMRM	ITT population
Figure 14.2.1.1	Change from baseline through Week 16 in pre-BD FEV1 measured in the clinic, LSM means (80% CI)	ITT population
Table 14.2.1.4	Change from baseline to Week 16 in pre-BD FEV1 (as measured in the clinic) treatment comparisons, MMRM - supportive analysis	ITT population

Figure 14.2.1.2	Change from baseline through Week 16 in pre-BD FEV1 measured in the clinic, LSMeans (80% CI) - supportive analysis	ITT population
Table 14.2.1.5	Change from baseline to Week 16 in pre-BD FEV1 (as measured in the clinic) treatment comparisons by subgroups, MMRM	ITT population
Figure 14.2.1.3	Change from baseline through Week 16 in pre-BD FEV1 measured in the clinic, LSMeans (80% CI) by subgroups	ITT population
Figure 14.2.1.4	Change in pre-BD FEV1 measured in the clinic at Week 16, MMRM - forest plot by subgroups	ITT population
Table 14.2.1.6	Change from baseline to Week 16 in pre-BD FEV1 (as measured in the clinic) treatment comparisons, MMRM - exploratory analysis	ITT population
Table 14.2.1.7	Change from baseline through Week 24 in pre-BD FEV1 (as measured in the clinic) treatment comparisons, MMRM	ITT population
Figure 14.2.1.5	Change from baseline through Week 24 in pre-BD FEV1 measured in the clinic, LSMeans (80% CI)	ITT population
Table 14.2.1.8	Change from baseline through Week 16 in post-BD FEV1 (as measured in the clinic) treatment comparisons, MMRM	ITT population
Figure 14.2.1.6	Change from baseline through Week 16 in post-BD FEV1 measured in the clinic, LSMeans (80% CI)	ITT population
Table 14.2.1.9	Change from baseline through Week 16 in FEV1% reversibility (as measured in the clinic) treatment comparisons, MMRM	ITT population

Figure 14.2.1.7	Change from baseline through Week 16 in FEV1% reversibility measured in the clinic, LSMeans (80% CI)	ITT population
Table 14.2.1.10	Change from baseline through Week 16 in pre-BD FEF25-75% (as measured in the clinic) treatment comparisons, MMRM	ITT population
Table 14.2.2.1	Home spirometry parameters 2-weekly means, summary statistics	ITT population

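### The exploratory acute-effect objective is worded as a comparison with placebo, but the SAP plans only descriptive summaries of the 4-hour FEV1 change and pre-specifies no treatment difference or interval

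*Protocol*

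**What the plan says.** **Objective.** Protocol Section 3 (Table 4) lists, among the exploratory objectives, "To assess the acute effect of MEDI3506 compared with placebo on pre-BD FEV1". The endpoint is the change in pre-BD FEV1 "from pre-administration of study intervention to 4 hours post-administration of MEDI3506 or placebo at Day 1". SAP Table 1 repeats both and does not give the endpoint the asterisk that marks endpoints left out of the CSR.

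**Method.** Protocol Section 9.4.2.2 names no analysis for this endpoint, and Section 9.4.5.3 leaves other exploratory analyses to the SAP. SAP Section 4.2.5.1 says that observed values and changes in pre-BD FEV1 "to 4-hours post administration of IP at Day 1 will also be summarised". SAP Section 3.1.4 adds only this: "For in-clinic spirometry pre-BD at day 1 timepoint at 4 hour post dose need also to be considered".

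**Outputs.** In SAP Appendix C, the entry that could hold the 4-hour data is Table 14.2.1.1, "Lung function parameters measured in clinic by visit, summary statistics", with its by-subgroup companion, Table 14.2.1.2. The treatment-comparison tables for clinic spirometry (14.2.1.3 to 14.2.1.10) run to Week 16 or Week 24. None is for 4 hours. SAP Section 6, which lists departures from the protocol, does not mention this objective.

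**The concern.** The question is comparative and the planned analysis is descriptive. The change from pre-dose to 4 hours within an arm combines any drug effect with shifts that affect every arm. The pre-dose test at SV4 starts between 6 and 11 AM and the second reading is at least four hours later (Protocol Section 8.1.1.1 and Table 2). Bronchodilator and controller medicines are withheld until all spirometry is complete (Protocol Section 6.5.3). The difference from placebo is what isolates the drug effect.

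If the plan does not say how that difference will be estimated, there are two risks. The CSR may address a stated comparative objective with arm summaries alone. Or the model, covariates and interval may be chosen after sponsor staff are unblinded at the primary data lock.

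**Working it through.** **1. Is the 4-hour change covered by any model in the SAP?**

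- SAP 4.1.2: the MMRM "will be used to fit change from baseline for continuous endpoints at each visit". Its uses for pre-BD FEV1 (4.2.4.1, 4.2.4.2, 4.2.4.4) run by visit to Week 16 or Week 24. None names the Day 1 4-hour timepoint.
- SAP 4.1.3: "An ANCOVA model will be used to analyse change from baseline for continuous endpoints collected at only one post-baseline visit". Pre-BD FEV1 is measured at many visits, the 4-hour reading is a second timepoint within SV4, and 4.2.5.1 does not refer to 4.1.3.
- The paragraph of 4.2.5.1 after the 4-hour sentence assigns an MMRM to post-BD FEV1. A model is named there when one is intended.
- Appendix C names ANCOVA where it is planned for a single post-baseline visit (sST2, cough measures, cough VAS). It has no such entry for 4 hours.

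**2. Is this the SAP's usual treatment of such objectives?** Other unredacted exploratory efficacy objectives that are worded as comparisons with placebo and kept in the CSR receive a model. Examples are oscillometry (4.2.6.1), reversibility (4.2.6.2), exacerbations (4.2.6.3), SNOT-22 (4.2.6.5), diary data and home spirometry (4.2.6.6), EDN and total IgE (4.2.8.2), and cough (4.2.8.3). PGI-BR is only summarised, but its objective is not comparative. The acute FEV1 objective is the exception.

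**3. The plan's own sample-size figure.** Inputs from Protocol Section 9.2: 72 per arm, difference 150 mL, SD 420 mL, one-sided 10%.

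- SE = 420 × √(2/72) = 420/6 = 70 mL.
- Power = Φ(150/70 − 1.2816) = Φ(0.861) = 0.805, or 0.804 with a noncentral t on 213 df.
- Randomised total = 216/0.95 = 227.4, rounded up to 228.

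The stated power of at least 80% and the 228 both reproduce.

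**4. What a 4-hour comparison would deliver at the same N.** The documents give no SD for the 4-hour change, so the SDs below are assumptions, except that 420 mL is borrowed from Week 16. Unadjusted SE = SD × √(2/72) = SD/6. The two-sided 80% half-width is 1.2816 × SE.

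| SD of 4-hour change (mL) | SE (mL) | 80% half-width (mL) |
|---|---|---|
| 150 (assumed) | 25.0 | 32 |
| 200 (assumed) | 33.3 | 43 |
| 300 (assumed) | 50.0 | 64 |
| 420 (borrowed) | 70.0 | 90 |

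Baseline adjustment would narrow these to the extent that the covariates explain the change.

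**The case against.** **The wording need not imply a contrast.** The safety objective is also stated as a comparison with placebo, and it is handled entirely by summaries by treatment group (SAP 4.2.7). Description beside the placebo arm is therefore one way this plan meets such an objective. That is fair. However, the efficacy objectives listed in the working above follow the opposite pattern, and this is one of them.

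**The placebo arm is there.** The first sentence of SAP 4.2.5.1 summarises clinic lung function by treatment group, and it is reasonable to read the 4-hour sentence the same way. SAP 4.1 includes n, mean and SD among the standard statistics. A reader can subtract the placebo mean and compute an unadjusted 80% interval. This stands. One might infer that the plan leaves no way to separate drug effect from time-of-day or withholding shifts. The documents do not support that, because the placebo arm carries the same shifts and is shown. The loss is the baseline adjustment and the pre-specification.

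**The general ANCOVA rule might apply.** The acute effect is listed as its own endpoint with one post-dose reading, so 4.1.3 could be stretched to cover it. This is arguable, but nothing in 4.2.5.1 invokes it. Absence from Appendix C is not conclusive alone: 4.2.8.3 promises cough figures that Appendix C does not list. It does agree with the text of 4.2.5.1.

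**It is one exploratory endpoint.** True, and this limits the weight of the point.

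**Conclusion.** The gap is real and modest. The protocol and SAP pose a comparison with placebo at 4 hours. The SAP plans descriptive summaries, pre-specifies no adjusted difference or interval, and does not declare this as a departure.

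Two stronger readings should be avoided. First, it is tempting to say that the data could rule an acute effect in or out well below 150 mL. That depends on an SD the documents do not give. The half-width is about 32 to 64 mL under the assumed SDs, but about 90 mL with the only FEV1 SD documented, and these are 80% intervals. Second, a one-sided p-value would not answer a worry about acute harm. The hypotheses in SAP 4.1.1 point towards benefit, so the interval is the output that would show a fall.

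Importance is low to moderate. No primary or secondary result, alpha allocation or sample size is affected, and the data are collected either way.

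**What to change.** In SAP Section 4.2.5.1, add an ANCOVA of the change in FEV1 from pre-dose to 4 hours on Day 1, with treatment, pre-dose FEV1 and the other Section 4.1.3 covariates (background medication use, geographic region, baseline ICS total daily dose). Report each MEDI3506 dose minus placebo with a two-sided 80% CI as the main output. State that any one-sided p-value is nominal and outside the testing hierarchy. Add the matching treatment-comparison table to Appendix C.

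If the sponsor prefers to keep the analysis descriptive, the minimum is a line in SAP Section 6 saying that this comparative objective will be addressed by summaries only.

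The cost is a few lines of SAP text and one table. It needs no new data or visits and no change to sample size. It should be settled before the primary data lock, after which sponsor staff are unblinded.

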4 STUDY DESIGN

4.1 Overall Design

Study D9181C00001 is a Phase II, randomised, double-blind, placebo-controlled, parallel-group, proof-of-concept study to evaluate the efficacy, safety, PK and immunogenicity of MEDI3506 in adult participants with uncontrolled moderate-to-severe asthma on SOC.

Approximately 228 participants will be randomised in a 1:1:1 ratio to achieve 216 evaluable participants. Participants will receive CCI mg MEDI3506, CCI mg MEDI3506, or placebo CCI by SC injection for a total of C doses. The randomisation will be stratified according to cough sub-study participation. Note that the exploratory cough sub-study may not be activated in all countries.

Participants who fail screening can be re-screened.

Participants will be enrolled in this study for up to 29 weeks. The study comprises of 3 periods including the screening period of up to 5 weeks, an intervention period of 16 weeks, and a follow-up period of 8 weeks.

Safety data from this study will be provided to the MEDI3506 DSMB (see Appendix A 4).

Screening Period

- Participants will sign ICF and be assessed for study eligibility at SV1 (Sections 5.1 and 5.2).
- Participants assessed to have uncontrolled asthma at SV1 will undergo further baseline assessments at SV1 (see Table 1). Participants will then record adherence to their SOC asthma controller and reliever medication for a minimum period of 14 days before returning for SV2.
- At SV2, participants whose asthma remains uncontrolled despite acceptable adherence to asthma controller medication ($\geq 70\%$ adherence [days] to controller medication documented in eDiary and $ACQ-6 \geq 1.5$) will undergo further screening assessments (including echocardiogram). Participants who continue to meet all eligibility criteria will be asked to attend SV4 (randomisation) 6 to 14 days following SV2.
 - A subset of participants (up to $n = 60$, see Section 9.2 for details) who have provided optional informed consent to participate in the sub-study, will also undergo 24-hour objective cough monitoring at home, as part of an exploratory cough sub-study, commencing at SV2 and again at SV10.

Intervention Period

- Participants will be randomised at SV4 (Day 1).
- Study interventions will be administered CCI at CCI, as well as the final dose administered at CCI.
- The primary endpoint will occur at SV10 (Week 16 post initial dose of study intervention).
- During the intervention period, participants will be required to take their asthma controller therapy regularly, complete the eDiary and perform lung function tests using a spirometry device at home regularly.
- An automated alert to the participant and site will be triggered if there is a clinically significant deterioration in any of the eDiary data points (as defined in Section 8.1.5) for > 2 days, prompting the participant to contact the investigator for further assessment of a possible asthma exacerbation. Alerts will only be received by site when eDiary uploads/syncs on adequate mobile or broadband signal; therefore, participants may initiate contact with the investigator for assessment of possible exacerbation regardless of any prompts from the site, or the eDiary and spirometry.

Follow-up Period

- Participants who complete the 16-week intervention period visit will complete an 8-week post-treatment follow-up period.
- Participants will be required to take their SOC asthma controller medications throughout the follow-up period.

